3.6 Duration of Agent-specific treatment

In the absence of treatment delays due to adverse event(s), treatment may continue until one of the following criteria applies:

• Extraordinary Medical Circumstances: If at any time the constraints of this protocol are detrimental to the patient's health, protocol treatment should be discontinued. In this event submit forms according to the instructions in the MATCH Forms Packet.

- Patient withdraws consent.
- Patient experiences unacceptable toxicity.
- Non-protocol therapies are administered.
- Disease progression
- 3.7 Duration of Follow-Up

Refer to the MATCH Master Protocol for specifics on the duration of follow-up.

	Grou
ECOG-ACRIN	Cancer Research

0

Study Parameters Rev. 12/16 **4.**

Rev. 2/16 Rev. Add29

- Therapeutic Parameters for Osimertinib (AZD9291) Treatment 4.1
- In addition to the study parameters listed in the MATCH Master Protocol, the below parameters must also be performed for patients on osimertinib (AZD9291) treatment. NOTE:
- All assessments required prior to registration to treatment should be done ≤ 4 weeks prior to registration to Steps 1, 3, 5, 7, excluding the radiologic evaluation and electrocardiogram (ECG). NOTE:

÷
2
ŝ
Ř

			Treatme	ant		
	Test/Assessment	Prior to Registration to Treatment	Every Cycle, prior to treatment	Every 2 Cycles	End of Treatment	Follow Up ^F
	H&P, Weight, Vital signs ^A	×	٢×			×
	Performance status	×	٦×			×
	CBC w/diff, plts ^B	×	٦×			×
	Serum chemistry ^B	×	٦×			×
	Radiologic evaluation ^D	×		۵X		XF
	β-HCG ^c	×				
	Toxicity Assessment ^G		×		×	XF
	Pill Count/Diary ^H		×		×	
	ECGK	×	×			
	ECHO/Nuclear Study	×				
	Tumor biopsy and blood sample for MATCH Master Protocol ^E			×	×	
13	Eye evaluation ^L	×				
Ā	History and physical including vital signs and weight at the start of	asch cycle (up to 3 da	ive hefore start of ne	(הוטעט אין		

ryua (up ישי

Rev. Ad Rev. 3/1

	At end or all MATCH study treatments, plood specimens and/or research plopsy after consent and registration to Step 8 Please refer to Section 4 of the MATCH Master Protocol to determine whether the patient proceeds to the next screening step or to follow-up (with potential end of treatment biopsy for research purposes on Step 8). Samples are to be submitted as outlined in Section 9 of the MATCH Master Protocol. To order Step 2/4 Screening or Step 8 kits, complete the EAY131 Collection and Shipping Kit Order Form (See Appendix XII of the MATCH Master Protocol) and fax to [contact].
Rev. 2/16 ^{F.}	Every 3 months if patient is < 2 years from study entry, and every 6 months for year 3. Toxicity assessments and radiologic evaluations are not equired to be done during Follow Up if progression has been previously reported; however if an adverse event occurs post treatment that meets he SAE reporting requirements, it still must be reported via CTEP-AERS, even if progression has occurred.
Ċ	bite personnel should evaluate for toxicity and discuss treatment compliance with the patient in order to ensure the medication is taken correctly; his evaluation may be conducted by telephone or in person. The Toxicity Assessment is not required prior to Cycle 1, but is required every subsequent cycle.
Ξ	The pill calendar will be collected at the end of every cycle. The Pill Count/Diary is not required prior to Cycle 1, but is required every subsequent sycle.
Rev. 2/16 ^{I.}	An electrocardiogram must be done on C1D1 approximately 2 hours after receiving the first dose of osimertinib (AZD9291), on C1D8, and then on 01 of each subsequent cycle.
т ¥	⁻ or Cycle 1, if the following tests/assessments occurred within 7 days of Day 1, they do not need to be repeated at this timepoint: H&P, Weight, /ital Signs; Performance Status; CBC w/diff, plts; Serum chemistry; Concomitant Medications. Within 8 weeks of treatment assignment.
Rev. Add13 L.	² atients should be asked about eye symptoms at baseline. Patients with unexplained eye symptoms should be referred to an ophthalmologist for a full ophthalmic assessment.

Rev. Add13 5. Drug Formulation and Procurement

This information has been prepared by the ECOG-ACRIN Pharmacy and Nursing Committees.

Availability

NO STARTER SUPPLIES MAY BE ORDERED. Subjects must be enrolled and assigned to the treatment subprotocol prior to submitting the clinical drug request to PMB.

Drug Ordering: NCI supplied agents may be requested by eligible participating Investigators (or their authorized designee) at each participating institution. Pharmaceutical Management Branch (PMB) policy requires that drug be shipped directly to the institution where the patient is to be treated. PMB does not permit the transfer of agents between institutions (unless prior approval from PMB is obtained – see general information) The CTEP-assigned protocol number must be used for ordering all CTEPsupplied investigational agents. The eligible participating investigators at each participating institution must be registered with CTEP, DCTD through an annual submission of FDA Form 1572 (Statement of Investigator), NCI Biosketch, Agent Shipment Form, and Financial Disclosure Form (FDF).If there are several participating investigators at one institution, CTEP-supplied investigatoral agents for the study should be ordered under the name of one lead investigator at that institution.

Submit agent requests through the PMB Online Agent Order Processing (OAOP) application (https://ctepcore.nci.nih.gov/OAOP). Access to OAOP requires the establishment of a CTEP Identity and Access Management (IAM) account (https://ctepcore.nci.nih.gov/iam/) and the maintenance of an "active" account status, a "current" password, and an active person registration status.

NCI Supplied Agent(s) – General Information

Questions about drug orders, transfers, returns, or accountability should be addressed to the PMB by calling [contact] Monday through Friday between 8:30 AM and 4:30 PM Eastern Time or email [contact] anytime.

Drug Returns: All undispensed drug supplies should be returned to the PMB. When it is necessary to return study drug (e.g., sealed bottles remaining when PMB sends a stock recovery letter), investigators should return the study drug to the PMB using the NCI Return Agent Form available on the NCI home page (http://ctep.cancer.gov).

Rev. 12/16 **Drug Accountability:** The investigator, or a responsible party designated by the investigator, must maintain a careful record of the receipt, disposition, and return of agent received from the PMB using the NCI Investigational Agent Accountability Record Form for Oral Agents available on the NCI home page (http://ctep.cancer.gov). Maintain separate NCI Investigational Agent Accountability Records for each agent, strength, formulation and ordering investigator.

Rev. 3/17 **Investigator Brochure Availability:** The current versions of the IBs for PMB-supplied agents will be accessible to site investigators and research staff through the PMB Online Agent Order Processing (OAOP) application. Access to OAOP requires the establishment of a CTEP Identity and Access Management (IAM) account and the maintenance of an "active" account status, a "current" password, and active person registration status. Questions about IB access may be directed to the PMB IB coordinator at [contact].

		 		
Rev. 12/16	5.1	Osimertini	b (AZD9291) (NSC #781254)	
Rev. Add29		5.1.1	Other Names	
			Tagrisso™, AZD9291 mesylate	
		5.1.2	Classification	
			Epidermal growth factor (EGFR) inhibitor	
		5.1.3	Mode of Action	
			Osimertinib (AZD9291) is a potent, oral, irreversible, tyrosine kinase inhibitor (TKI) of epidermal growth factor receptor (EGFR) mutation- positive (EGFRm) and T790M mutation-positive forms of EGFR	
		5.1.4	Storage and Stability	
			Storage: Store at room temperature 20° to 25°C (68° to 77°F), excursions permitted between 15 to 30°C (59 to 85°F).	
			If a storage temperature excursion is identified, promptly return osimertinib (AZD9291) to controlled room temperature and quarantine the supplies. Provide a detailed report of the excursion (including documentation of temperature monitoring and duration of the excursion) to [contact] for determination of suitability.	
			Stability: Refer to the package label for expiration	
		5.1.5	Dose Specifics	
			The dose will be 80mg orally once daily continuously.	
		5.1.6	How Supplied	
			Osimertinib (AZD9291) tablets are supplied by AstraZeneca and distributed by the Pharmaceutical Management Branch, CTEP/DCTD/NCI. Tablets are packaged in 30-count bottles with mannitol, microcrystalline cellulose, low-substituted hydroxypropyl cellulose and sodium stearyl fumarate as inactive ingredients in the following strengths:	
			 80 mg tablets: beige, oval and biconvex tablet marked with "AZ 80" on one side and plain on the reverse. 	
			 40 mg tablets: beige, round and biconvex tablet marked with "AZ 40" on one side and plain on the reverse. 	
			The tablet coating contains polyvinyl alcohol, titanium dioxide, macrogol 3350, talc, ferric oxide yellow, ferric oxide red and ferric oxide black.	
		5.1.7	Route of Administration	
			Take by mouth with or without food. If a dose of osimertinib (AZD9291) is missed or vomited, do not make up the missed dose and take the next dose as scheduled.	

Rev. 12/16

5.1.8 Incompatibilities

The main metabolic pathways of osimertinib (AZD9291) are oxidation (predominantly CYP3A4) and dealkylation in vitro. Avoid concomitant use of strong CYP3A4 inducers. CYP3A4 inhibitors are not likely to affect the exposure of osimertinib (AZD9291). Based on in vitro studies, osimertinib (AZD9291) is a competitive inhibitor of CYP 3A4/5 but not CYP1A2, 2A6, 2B6, 2C8, 2C9, 2C19, 2D6 and 2E1 at clinically relevant concentrations. Osimertinib (AZD9291) is an inducer of CYP1A2. Use caution with coadministration of CYP 3A4/5 and 1A2 substrates. Osimertinib (AZD9291) is a substrate of BCRP and P-gp but is unlikely to result in clinically relevant drug interactions. Osimertinib (AZD9291) is not a substrate of OATP1B1 and OATP1B3 and does not inhibit OAT1, OAT3, OATP1B1, OATP1B3, OCT2, MATE1 and MATE2K at clinically relevant concentrations. Based on in vitro data, osimertinib (AZD9291) is an inhibitor of BCRP and may increase the exposure of BCRP substrates. Osimertinib (AZD9291) does not inhibit P-gp at clinically relevant concentrations but has the potential to increase exposure of sensitive substrates. Avoid use of osimertinib (AZD9291) in patients with congenital long QT syndrome. For patients with normal QT interval at the trial enrollment, avoid use of concomitant drugs that are known to prolong QT interval and use caution with drugs that may prolong QT interval. Refer to a frequently updated drug information reference and to the protocol for appropriate cardiac monitoring. 5.1.9 Side Effects See Section 3.3 for side effects. 5.1.10 Patient Care Implications Advise patients of reproductive potential to use effective methods of contraception. Patients of child-bearing potential must use an appropriate double barrier method of birth control (such as female use

of a diaphragm, intrauterine device (IUD), sponge and spermicide, in addition to the male use of a condom) or involve female use of prescribed "birth control pills" or a prescribed birth control implant. Both double barrier contraception and birth control pill or implants must be used for at least one week prior to the start of the study and continuing for 16 weeks after the last dose of the study drugs.

Appendix I

Rev. 12/16, 3/17 Rev. Add29

Patient Pill Calendar

Pill Calendar Directions

- 1. Take your scheduled dose of each tablet.
- 2. If you forget, the missed tablets will not be taken later.
- 3. Please bring the empty bottle or any leftover tablets and your pill calendar to your next clinic visit.
- 4. Take AZD9291 once daily by mouth, with or without food.
- 5. Swallow tablets whole. Do not crush or chew tablets.
- 6. Store tablets at room temperature.

Patient Pill Calendar

This is a calendar on which you are to record the time and number of tablets you take each day. You should take your scheduled dose of each tablet. Note the times and the number of tablets that you take each day. If you develop any side effects, please record them and anything you would like to tell the doctor in the space provided. Bring any unused tablets and your completed pill calendar to your doctor's visits.

DAY	Month	Date Day	Year	Time tablets taken	Dose taken	Use the space below to make notes about things you would like to tell the doctor (including unusual symptoms you experience, other medicine you have taken and anything else you think would be of interest.)
1						
2						
3						
4						
5						
6						
7						
8						
9						
10						
11						
12						
13						
14						
15						
16						
17						
18						
19						
20						
21						
22						
23						
24						
25						
26						
27						
28						

Δ7D9291

Patient Signature: _____ Date: _____

Molecular Analysis for Therapy Choice (MATCH) MATCH Treatment Subprotocol E: Osimertinib (AZD9291)

Appendix II

Rev. Add13 Rev. Add29

Guidance Regarding Potential Interactions with Concomitant Medications

The use of any natural/herbal products or other "folk remedies" should be discouraged, but use of these products, as well as use of all vitamins, nutritional supplements, and all other concomitant medications must be recorded in the electronic case report form (eCRF).

1. Drugs Inducing CYP3A4 Metabolism That AstraZeneca Strongly Recommend Are Not Combined With Osimertinib

Osimertinib is metabolised by CYP3A4 and CYP3A5 enzymes.

A drug-drug interaction study of osimertinib evaluated in patients showed that there is potential for osimertinib being a victim when co-administered with strong inducers of CYP3A4 (osimertinib concentrations are decreased when co-dosed with rifampicin).

The following potent inducers of CYP3A4 must not be used during this study for any patient receiving osimertinib.

D1 Drugs Inducing CYP3A4

Contraindicated drugs	Withdrawal period prior to osimertinib start
Carbamazepine, phenobarbital, phenytoin, rifampicin, rifabutin, rifapentin St John's Wort	3 weeks
Phenobarbitone	5 weeks

This list is not intended to be exhaustive, and a similar restriction will apply to other agents that are known to strongly modulate CYP3A4 activity. Appropriate medical judgment is required.

2. Medicines Whose Exposures May be Affected by Osimertinib That AstraZeneca Considers May be Allowed With Caution

Osimertinib may increase the concentration of sensitive breast cancer resistance protein (BCRP) substrates (concentration of the sensitive BCRP substrate, rosuvastatin, is increased).

Warning of possible interaction	Advice
Rosuvastatin	Drugs are permitted but caution should be exercised and patients
Sulfasalazine	full prescribing information for all drugs prior to co-administration
Doxorubicin	with osimertinib.
Daunorubicin	
Topotecan	

D2 Exposure, Pharmacological Action and Toxicity May be Increased by Osimertinib

3. Drugs That May Prolong QT Interval

The drugs listed in this section are taken from information provided by The Arizona Center for Education and Research on Therapeutics and The Critical Path Institute, Tucson, Arizona and Rockville, Maryland. Ref: http://www.arizonacert.org/medical-pros/drug-lists/drug lists.htm.

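### Appendix II, table D1, lists one drug under two names with different withdrawal periods before osimertinib: phenobarbital 3 weeks, phenobarbitone 5 weeks

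*Protocol*

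**What the plan says.** Section 1 of Appendix II explains that "there is potential for osimertinib being a victim when co-administered with strong inducers of CYP3A4" and gives the direction of the effect from an interaction study: "osimertinib concentrations are decreased when co-dosed with rifampicin". It then introduces table D1 with a prohibition: "The following potent inducers of CYP3A4 must not be used during this study for any patient receiving osimertinib".

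Table D1 has two columns, the contraindicated drugs and the "Withdrawal period prior to osimertinib start". It has two rows:

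- 3 weeks: "Carbamazepine, phenobarbital, phenytoin, rifampicin, rifabutin, rifapentin St John's Wort"
- 5 weeks: "Phenobarbitone"

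Below the table, the protocol says the list is not complete, that "a similar restriction will apply to other agents that are known to strongly modulate CYP3A4 activity", and that "Appropriate medical judgment is required".

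Two other places bear on the table. Eligibility criterion 2.1.9 excludes patients who are currently on potent CYP3A4 inducers and refers to Appendix II. Section 5.1.8 advises against strong CYP3A4 inducers alongside osimertinib. Neither gives a withdrawal period.

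**The concern.** Phenobarbital and phenobarbitone are two naming conventions for one substance. The protocol does not say so, but this is basic drug nomenclature and depends on no particular source. Read that way, table D1 gives two different waiting times for the same drug, and nothing in the protocol ranks them.

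What is at stake is exposure at the start of treatment. A withdrawal period makes sense only if the inducer's effect is taken to outlast its last dose. If 5 weeks is the period needed, a patient started at 3 weeks may begin osimertinib while its concentrations are still being lowered. Two sites could also handle identical patients differently, each following a row of the table.

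**Working it through.** No sample size, power or error rate is involved. The check is a comparison of the two rows and a conversion of units.

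**Inputs, all from Appendix II, table D1**

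- Row 1, which contains phenobarbital: 3 weeks.
- Row 2, which contains only phenobarbitone: 5 weeks.
- Assumption from general nomenclature: the two names denote one drug.

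**Arithmetic**

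1. Row 1 in days: 3 × 7 = 21.
2. Row 2 in days: 5 × 7 = 35.
3. Difference: 35 − 21 = 14 days.
4. Start days, counted from the last dose, that meet row 1 but fail row 2: day 21 to day 34, so 34 − 21 + 1 = 14 days.
5. Example: a patient who stopped 4 weeks (28 days) before the planned start is 28 − 21 = 7 days past the first limit and 35 − 28 = 7 days short of the second.

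| Start, days after last dose | 3-week row | 5-week row |
|---|---|---|
| Before day 21 | fails | fails |
| Day 21 to 34 | meets | fails |
| Day 35 or later | meets | meets |

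Only the middle band is in conflict. A 5-week wait satisfies both rows; a 3-week wait falls 14 days short of the second.

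**Is the conflict resolved elsewhere?**

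- No footnote in table D1 distinguishes the two names or explains the two periods.
- The text under the table extends the restriction to agents that are not listed. It does not choose between two entries that are.
- Criterion 2.1.9 and Section 5.1.8 give no period that could settle it.
- The rows look intact in the extracted text, each with its own drug cell and its own period, so a broken table is not the likely explanation. This is current text, not a record of changes.

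**What cannot be computed**

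The protocol gives neither the number of patients who will come off this drug nor the size of any fall in exposure. It gives only the direction, for rifampicin.

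**The case against.** The strongest reply is that the table can be obeyed in full, because 5 weeks meets both rows. The 5-week row also stands directly beneath the 3-week row in a two-row table, so an attentive reader will see it. A reader might infer that a site finding phenobarbital in the first row has no warning of a longer period. The layout does not support that. What remains is that the reader must recognise the second name as the same drug and then decide unaided which period applies.

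A reader might also infer that table D1 by itself settles eligibility. The protocol does not go that far. Criterion 2.1.9 excludes only current use and states no waiting time. The prohibition that introduces the table concerns use during the study. The withdrawal period stands only in a column of an appendix titled as guidance, under a heading that frames the inducer list as a strong recommendation from the manufacturer, and the section closes with an appeal to medical judgment. This makes a wrong eligibility decision less likely, but it does not reconcile the two rows.

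The impact is also limited. Only patients who stopped this one drug 21 to 34 days before starting are concerned, in a subprotocol with an accrual goal of 35. Dosing is continuous, and disease is re-measured every 2 cycles at first, 2 × 28 = 56 days. That objection stands and fixes the severity as minor.

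Finally, a reader might see a second conflict in table D4, which permits fosphenytoin after a stable period while table D1 bars phenytoin. The protocol does not establish one. The link between the two drugs is pharmacology it does not state. The conflict also needs a literal reading of D4's introductory sentence that is probably not the intended one. The extension clause under table D1, criterion 2.1.9 and Section 5.1.8 can already be read to exclude the drug.

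**Conclusion.** The inconsistency is real: one drug has two withdrawal periods 14 days apart, and no rule says which prevails. High confidence attaches to that textual conflict. It rests on one assumption from outside the document, that the two names mean the same drug.

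The consequence is modest. A start between day 21 and day 34 could be accepted under one row although the other treats it as too early, with a risk of reduced osimertinib exposure. The size of that risk is unknown, and the patients concerned are probably few. The document does not support a claim that treatment results would be materially distorted, and no sample size, endpoint or error rate depends on this table. It is a minor internal inconsistency that should be corrected.

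**What to change.** In table D1, delete phenobarbital from the 3-week row and keep a single row: Phenobarbital (phenobarbitone), 5 weeks. The document does not show which period was intended. Five weeks is the sensible default because it satisfies both present rows. If the sponsor considers 3 weeks sufficient, it should confirm and justify that, and the drug should still appear only once.

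The change is a one-line text amendment. Its cost to a patient is a start up to 14 days later, 14 / 28 = half a treatment cycle, and only for someone coming off this drug who would otherwise have followed the 3-week row. Nothing else in the design changes.

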3.1 Drugs known to prolong QT interval

The following drugs are known to prolong QT interval or induce Torsades de Pointes and should not be combined with osimertinib. Recommended withdrawal periods following cessation of treatment with these agents are provided in the table.

D3 Drugs Prolonging QT Interval

Contraindicated drug	Withdrawal period prior to osimertinib start
Clarithromycin, droperidol, erythromycin, procainamide	2 days
Cisapride, disopyramide, dofetilide, domperidone, ibutilide, quinidine, sotalol, sparfloxacin, thioridazine	7 days
Bepridil, chlorpromazine, halofantrine, haloperidol, mesoridazine	14 days
Levomethadyl, methadone, pimozide	4 weeks
Arsenic trioxide	6 weeks ^a
Pentamidine	8 weeks
Amiodarone, chloroquine	1 year

a Estimated value as pharmacokinetics of arsenic trioxide has not been studied

3.2 Drugs that may possibly prolong QT interval

The use of the following drugs is permitted (notwithstanding other exclusions and restrictions) provided the patient has been stable on therapy for the periods indicated.

D4 Drugs That May Prolong QT Interval

Drug	Minimum treatment period on medication prior to osimertinib start
Alfuzosin, chloral hydrate, ciprofloxacin, dolasetron, foscarnet, galantamine, gemifloxacin, isridipine, ketoconazole, levofloxacin, mexiletine, nicardipine, octreotide, ofloxacin, ondansetron, quetiapine, ranolazine, telithromycin, tizanidine, vardenafil, venlafaxine, ziprasidone	2 days
Amantadine, amitriptyline, amoxapine, clozapine, doxepin, felbamate, flecainide, fluconazole, fosphenytoin, gatifloxacin, granisetron, imipramine, indapamide, lithium, moexipril/HCTZ, moxifloxacin, risperidone, roxithromycin, sertraline, trimethoprin-sulfa, trimipramine, voriconazole	7 days

Drug	Minimum treatment period on medication prior to osimertinib start
Azithromycin, citalopram, clomipramine, itraconazole, nortriptyline, paroxetine, solifenacin, tacrolimus	14 days
Fluoxetine	5 weeks
Protriptyline	6 weeks
Tamoxifen	8 weeks

Molecular Analysis for Therapy Choice (MATCH) MATCH Treatment Subprotocol E: Osimertinib (AZD9291)

Rev. 12/16	Appendix III			
Rev. Add13 Rev. Add25 Rev. Add29	PATIENT CLINICAL TRIAL WALLET CARD			
NGV. AUUZƏ	NH) NATIONAL CANCER INSTITUTE CLINICAL TRIAL WALLET CARD Show this card to all of your healthcare providers and keep it with you in case you go to the emergency room.			
	Patient Name:			
	Diagnosis:			
	Study Doctor:			
	Study Doctor Phone #:			
	NCI Trial #:			
	Study Drug(S):			
	For more information: [name] cancer.gov clinicaltrials.gov			

Molecular Analysis for Therapy Choice (MATCH) MATCH Treatment Subprotocol E: Osimertinib (AZD9291)

Rev. Add13 Rev. Add25 Rev. Add29

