		Date of ECG:	
Rev. 2/16	2.1.4	Patients must have an ECHO or a r Pass) within 4 weeks prior to registr ventricular ejection fraction (LVEF) (LLN). If the LLN is not defined at a the patient to be eligible.	nuclear study (MUGA or First ration and must not have a left < institutional lower limit of normal site, the LVEF must be > 50% for
		Date of ECHO/Nuclear Study:	
Rev. Add13	2.1.5	Patients must not have known hype (AZD9291) or compounds of similar or any of the inactive excipients of t	ersensitivity to osimertinib r chemical or biologic composition the tablets.
	2.1.6	Patient must not have received osir 1686, HM61713, EGF816 or ASP82	mertinib (AZD9291), WZ4002, CO- 273 previously.
	2.1.7	Patients known to harbor germline excluded from the study. Prospectivnot required.	EGFR T790M mutations are ve testing for germline mutations is
Rev. Add13	2.1.8	Patients must not have a history of pulmonary fibrosis, organizing pneu obliterans), drug-induced pneumon radiation pneumonitis requiring ster pneumonitis on screening chest con History of radiation pneumonitis in t permitted.	interstitial lung disease, idiopathic umonia (eg, bronchiolitis itis, idiopathic pneumonitis, roids, or evidence of active mputerized tomography (CT) scan. the radiation field (fibrosis) is
Rev. Add13	2.1.9	Patients must not currently be receip CYP3A4 inducters or medications " as defined in Appendix II . Drugs that interval, as defined in Appendix II , a been stable on therapy for the perior medication.	iving treatment with potent known to prolong" the QT interval at "may possibly prolong" the QT are permitted if the patient has od indicated for the specific
Rev. Add13	2.1.10	Patients must agree to not donate s treatment until at least 4 months aft treatment.	sperm from the start of protocol ter the last dose of protocol
		Physician Signature	Date

OPTIONAL: This signature line is provided for use by institutions wishing to use the eligibility checklist as source documentation.

Rev. Add29 3. Osimertinib (AZD9291) Treatment Plan

3.1 Administration Schedule

Osimertinib (AZD9291) is given orally. The dose will be 80mg orally once daily continuously. A cycle is defined as 28 days.

Patients should be instructed that if they vomit after taking a dose, then they must not "make it up" with an extra dose, but instead, resume subsequent doses as prescribed. Any missed dose should be skipped and dosing resumed with subsequent doses.

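### Appendix II table D4 permits fosphenytoin by name, although table D1 prohibits phenytoin, the drug it becomes in the body

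*Protocol*

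**What the plan says.** **The prohibition.** Protocol, Appendix II, item 1 introduces table D1 with "The following potent inducers of CYP3A4 must not be used during this study for any patient receiving osimertinib". The 3-week withdrawal row of D1 begins "Carbamazepine, phenobarbital, phenytoin, rifampicin, rifabutin, rifapentin". A note under the table says that the list is not exhaustive, that "a similar restriction will apply to other agents that are known to strongly modulate CYP3A4 activity", and that medical judgment is needed. The stated reason is a drug interaction study in patients: "osimertinib concentrations are decreased when co-dosed with rifampicin".

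Section 2.1.9 excludes patients currently on potent CYP3A4 inducers or on drugs known to prolong QT. Its text is scrambled in the copy at hand, but the rule is legible. Section 5.1.8 advises avoiding strong CYP3A4 inducers.

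**The permission.** Appendix II, item 3.2 introduces table D4 with "The use of the following drugs is permitted (notwithstanding other exclusions and restrictions"), on condition that the patient has been stable on the drug for the period shown. The 7-day row includes "doxepin, felbamate, flecainide, fluconazole, fosphenytoin, gatifloxacin". The column gives a minimum time on the drug before osimertinib starts, not a time off it. Section 2.1.9 also allows drugs that may possibly prolong QT on these terms and refers to Appendix II for them.

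**The concern.** Fosphenytoin is converted to phenytoin in the body, so a patient who takes it is exposed to a drug that D1 prohibits. D4 nevertheless names it as permitted and prefaces the list with a clause that, taken literally, sets other restrictions aside.

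The name fosphenytoin appears only in the permitted list. To reach the prohibition, a site must recognise the link to phenytoin or apply the catch-all under D1. A site that only looks up the name gets the wrong answer.

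What is at stake is osimertinib exposure. The protocol restricts strong inducers because one of them, rifampicin, lowered osimertinib concentrations. A patient admitted on the strength of D4 could be under-exposed from the first dose.

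**Working it through.** No sample size, power or error rate is involved, so there is no figure of the plan to reproduce. The check sets the rules side by side.

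| Place | Drug or class | Rule | Period before osimertinib start |
|---|---|---|---|
| Appendix II, D1 | Phenytoin, by name | Prohibited during the study | 3 weeks **off** |
| Appendix II, note under D1 | Other strong CYP3A4 modulators | Similar restriction | Not stated |
| Section 2.1.9 | Potent CYP3A4 inducers | Patient excluded | Not legible as a separate period |
| Section 5.1.8 | Strong CYP3A4 inducers | Avoid | Not stated |
| Appendix II, D4 | Fosphenytoin, by name | Permitted if stable | At least 7 days **on** |

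1. *Link between the two names.* Fosphenytoin is a prodrug of phenytoin. This premise is basic pharmacology and comes from outside the protocol. Everything else in the table is protocol text.
2. *Compatibility.* D1 asks for 3 × 7 = 21 days without phenytoin before osimertinib, and none during the study. D4 asks that the patient be on fosphenytoin for at least the 7 days up to the start. Given step 1, a patient who meets D4 cannot be in the state that D1 requires for phenytoin. This is a logical conflict, and the day counts are not an effect size.
3. *The clause in D4 read as written.* *Notwithstanding* means *despite*, so D4 would displace D1 for every drug that it lists.
4. *The clause read as* subject to. D1 and 2.1.9 then prevail. D4 is no longer an opposite rule, but it still names as permitted a drug that the inducer rules exclude.
5. *Is there a carve-out?* None was found. No text removes fosphenytoin from D4 or refers the reader from it to D1.
6. *Likely origin.* Appendix II, item 3 states: "The drugs listed in this section are taken from information provided by The Arizona Center for Education and Research on Therapeutics" (and a partner institute). A list compiled for QT risk would not have been screened for CYP3A4 induction. This is an inference.

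**The case against.** The strongest case on the other side is that the protocol already excludes this patient. Section 2.1.9 is cumulative: satisfying its QT part does not cancel its inducer part. Section 2 allows no waiver of any eligibility criterion. The note under D1 reaches strong modulators that are not listed and calls for medical judgment. D4 stands under a QT heading, so its permission is naturally read as answering the QT question alone.

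Much of this stands. A reader might infer from the word *notwithstanding* that the protocol means to override its inducer prohibition. The documents do not support that: such an override would clash with the no-waiver rule in Section 2, and the list comes from an outside QT source. The objection does not cure the table, however. Section 2.1.9 itself sends sites to Appendix II for the permission, and the only entry there under the drug's own name says yes. A general catch-all is a weak guard against a specific permission.

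Other limits also stand:

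- No drug is named in both tables, and the conflict needs the prodrug fact.
- Section 5.1.8 says to avoid strong inducers, which is softer than a prohibition. Only D1 and 2.1.9 prohibit.
- A reader might infer a measurable loss of efficacy or a biased response rate. The protocol gives no size of interaction for rifampicin, phenytoin or fosphenytoin and no count of users, so no such claim can be made.
- Fosphenytoin is an injectable drug, normally given short term (again general pharmacology), so 7 stable days on it before entry is an unlikely case. It is not impossible: Section 2.1.2 admits malignancies broadly, and Section 1.2 lists the central nervous system among the sites where T790M has been recorded, so anticonvulsant use is plausible.
- Section 2.1.1 also imports eligibility criteria from the MATCH Master Protocol, which is not at hand and may restrict concomitant drugs further.

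**Conclusion.** The point holds as a minor inconsistency in a stated rule. D4 lists as permitted a drug whose active form D1 prohibits, and the introductory clause of D4 makes this worse by appearing to set the prohibition aside. On either reading of that clause the entry needs correcting: read literally it contradicts D1, and read charitably it misleads.

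The possible consequence is lower osimertinib exposure in a rare patient. The accrual goal is 35, and the number taking fosphenytoin is not given; it is likely none or very few. No statistical figure changes.

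The conclusion rests on two assumptions: that fosphenytoin delivers phenytoin, which is not in the document, and that induction by phenytoin matters for osimertinib, which D1 itself implies by listing it.

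**What to change.** 1. Delete fosphenytoin from the 7-day row of D4 and add it to D1 beside phenytoin, with the same 3-week withdrawal. This alone removes the conflict.
2. Replace the parenthesis in the sentence above D4 with: *subject to the restriction on strong CYP3A4 inducers in D1 and 2.1.9*.

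The second change should be no broader than this. Making D4 subject to D1 as a whole would bring in the catch-all, which speaks of agents that strongly *modulate* CYP3A4. That could be read to ban the CYP3A4 inhibitors in D4, such as ketoconazole, itraconazole and voriconazole, although Section 5.1.8 says that CYP3A4 inhibitors are unlikely to affect osimertinib exposure.

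The cost is one drug name moved and one phrase replaced. Data collection, sample size and analysis do not change. A patient on fosphenytoin would have to be off it for 3 weeks before starting, as D1 already requires for phenytoin.
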